12.0 Data Reporting/Protocol Deviations

12.1 Confidentiality and Storage of Records

The original data collection forms will be stored at the originating institution in a secure location. Study data will be entered into an electronic case report form (eCRF) using an encrypted, password protected, secure electronic data capture (EDC) application that meets all HIPAA requirements. When results of this study are reported in medical journals or at meetings, identification of those taking part will not be disclosed. Medical records of subjects will be securely maintained in the strictest confidence, according to current legal requirements. They will be made available for review, as required by the FDA, HHS, or other authorized users such as the NCI, under the guidelines established by the Federal Privacy Act and rules for the protection of human subjects.

12.2 Subject Consent Form

The original signed and dated Informed Consent form, HIPAA research authorization form, and the California Experimental Subject's Bill of Rights will be stored in the research record. At the time of registration, a copy of the original signed and dated consent documents will be available to the patient and another copy will be stored in the medical record. All Institutional, NCI, Federal, and State of California requirements will be fulfilled.

12.3 Data Collection Forms and Submission Schedule

All data will be collected using Medidata EDC electronic case report forms.

12.3.1 Eligibility Checklist

The Eligibility Checklist must be completed by a protocol nurse or clinical research associate and signed by an authorized investigator prior to registering the subject. See Section 4.3 for the registration procedure.

12.3.2 Prior Therapy Forms and On-Study Forms

Within two weeks of registration, the clinical research associate will submit Prior Therapy Forms and On-Study Forms.

12.3.3 Treatment Forms, Adverse Event Collection Forms, Response/Off Study/Follow Up Forms

Within four weeks of completion of therapy, the clinical research associate will submit the Treatment Forms. Completed adverse events collection forms are due within four weeks of assessments per study calendar (refer to Section 10.0). Response/Follow Up/Off Study Forms are to be submitted within four weeks of the patient being evaluated for response and/or new follow up information is obtained.

12.4 Protocol Deviations

12.5 Deviation Policy

This protocol will be conducted in accordance with COH's "Clinical Research Protocol Deviation Policy" located at <http://www.coh.org/dsmc/Documents/Institutional%20Deviation%20Policy.pdf>.

Deviations from the written protocol that could increase patient risk or alter protocol integrity require prior IRB approval of a single subject exception (SSE) request. In addition, if contractually obligated, the sponsor must also approve the deviation. IRB pre-approved SSE protocol modifications are considered an amendment to the protocol and not a deviation. The submission of a deviation report is not required.

Brief interruptions and delays may occasionally be required due to travel delays, airport closure, inclement weather, family responsibilities, security alerts, government holidays, etc. This can also extend to complications of disease or unrelated medical illnesses not related to disease progression. The PI has the discretion to deviate from the protocol when necessary so long as such deviation does not threaten patient safety or protocol scientific integrity. Examples include, but are not limited to: a) dose adjustments based on excessive patient weight; b) alteration in treatment schedule due to non-availability of the research participant for treatment; c) laboratory test results which are slightly outside the protocol requirements but at levels that do not affect participant safety. These instances are considered to be deviations from the protocol. A deviation report will be submitted to the DSMC/IRB within five days.

12.5.1 Reporting of Deviations

All deviations will be reported to the COH DSMC within five days. The DSMC will forward to report to the IRB following review.

12.5.2 Resolving Disputes

The COH Investigational Drug Service (IDS) cannot release a research agent that would cause a protocol deviation without approval by the PI. Whenever the protocol is ambiguous on a key point, the IDS should rely on the PI to clarify the issue.

In situations where there is misperception or dispute regarding a protocol deviation among the persons involved in implementing the protocol, it is the responsibility of the PI to resolve the dispute and the PI may consult with the DSMC chair (or designee) to arrive at resolution.

13.0 Statistical Considerations

13.1 Study Design

This is a randomized Phase II study. The primary endpoint is to assess the feasibility, based on percent able or willing to receive all three infusions of Sipuleucel-T immunotherapy, when combining Sipuleucel-T with radiation therapy to a single site of metastasis delivered one week prior to beginning of Sipuleucel-T therapy. The ability to deliver three infusions of Sipuleucel-T, reflects the ability to collect adequate numbers of CD54+ cells for the generation of Sipuleucel-T, and tolerability reflected in the patient's willingness or ability to receive the three infusions. Secondary endpoints will include toxicity, and measurements of immune responses to PAP, PA2024 and PSA and radiologic responses to therapy with Sipuleucel-T +/- external beam radiation therapy to single metastasis.

13.2 Sample Size Accrual Rate

Patients with metastatic castration-resistant prostate cancer who are candidates for Sipuleucel-T immunotherapy. Total Sample size 50. Anticipated accrual is 2-3 patients a month. Likely duration of the study is 2 years. Randomization is 1:1.

13.3 Statistical Analysis Plan

Primary Endpoint: Previous publications suggest 8% were unable or unwilling to receive all three infusions of Sipuleucel-T. We will stop accrual at any time if more than 2 patients are unable to receive all three infusions and more than 30% of the patients are unable to receive all three infusions. This rule has a 4% of stopping if 8% are unable or unwilling to receive all three infusions, and a 82% chance of stopping early if 33% are unable or unwilling to receive all three infusions (based on 1000 simulations). In addition, if 3 patients in the first 10 are unable to initiate Sipuleucel-T immunotherapy on Arm B, the study will hold accrual pending review by the COH DSMB, sponsor and PI. This slightly increase the chance of early stopping (3 of 10 is not "more than 30%" but equal to 30%). Previous publications suggest only 2% of patients are unwilling or unable to begin Sipuleucel-T immunotherapy.

In addition, to the above stopping boundaries, there will be a safety review of the toxicities after 10 patients have been treated on Arm B, or after any grade 3 or higher treatment related toxicity on Arm B. These rules are in place to limit patient exposure to arm B if it proves poorly tolerated or too toxic.

Secondary Endpoint:

From the IMPACT study, titers of antibodies against prostatic acid phosphatase exceeded 400 in 28.5% of the patients treated with Sipuleucel-T. By having a control group, a Fisher's exact test with a 0.200 one-sided significance level will have 86% power to detect the difference between non-radiation proportion, 0.285 and a radiation-treated group proportion of 0.570 when the sample size in each group is 25. Also, with 25 patients, if the true proportion about 400 is 28.5% in the control arm, and 48.5% in the radiation arm, there is less than a 5% chance (~1% if the radiation proportion is 57%) that the observed proportion will be higher in the control arm, and there is an 85% chance that difference will exceed 8% between the two arms. In addition, secondary endpoints will include measurements of immune responses to PA2024 and PSA and radiologic responses to therapy with Sipuleucel-T +/- external beam radiation therapy to single metastasis.

As a result, by having a concurrently randomized control arm, initial comparisons of Arm A and Arm B including the influence of radiation on PSA kinetics and response, toxicity and tolerability will help

motivate future studies. For this exploratory secondary analysis, we will not include patients (if any) who do not start Sipuleucel-T immunotherapy, but will include all patients who start. A subset analysis of patients able to complete the planned three infusions will also be conducted.

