Eligible patients will meet the standard criteria for approved use of Sipuleucel -T. Patients will be randomized to receive standard Sipuleucel-T regimen (Arm A) or Sipuleucel-T preceded by radiation therapy to single site of metastatic disease (Arm B). In patients assigned to Arm B one metastatic site will be selected for radiation based primarily on the safety of radiation in that location. Radiation to bone metastases from L3 down to pelvis and femurs will be excluded provided that patients have other areas of metastases. Patients who have metastases only in the above locations (L3 down to pelvis and femurs) will be allowed provided that they have normal WBC and they will not receive radiation to more than 20% of the bone marrow. Patients will be treated with 300 cGy/day to 3000 cGy. Approximately 7 days after completion of radiation therapy patients will begin therapy with Sipuleucel-T autologous vaccine.
Endpoints:

Primary Endpoint:
 
The primary endpoint in this trial will be percent of patients able to receive all three infusions of Sipuleucel-T following radiation therapy. This endpoint reflects both tolerability and the ability to collect adequate numbers of CD54+ cells for the generation of Sipuleucel-T.
 
Secondary Endpoint:
 
Secondary endpoints will include measurements of immune responses to PAP, PA2024 and PSA and radiologic responses to therapy with Sipuleucel-T +/- external beam radiation therapy to single metastasis. Toxicity comparison between the two arms is also a secondary endpoint.

Sample Size:
Total Sample size is 50 randomized in a 1:1 fashion to Arm A and B. Anticipated accrual is 2-3 patients a month.
Estimated Duration of the Study
24 months
Summary of Subject Eligibility Criteria:

Inclusion Criteria:
 
Patients with metastatic castration-resistant prostate cancer who are candidates for Sipuleucel-T immunotherapy. Metastatic, minimally symptomatic or asymptomatic disease, ECOG PS 0-2
 
Exclusion Criteria:
 
Liver metastases, known brain metastases, > 2 prior chemotherapy regimens

Investigational Product Dosage and Administration:
Not Applicable. Radiation therapy constitutes investigational component of this study

Clinical Observations and Tests to be Performed:

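### The accrual stopping rule in 13.3 names no arm and counts only inability, so its wording does not secure the stated 82%, a figure that is correct for 25 Arm B patients with refusals counted

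*Combined protocol and SAP*

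**What the plan says.** Section 13.3 (Primary Endpoint) sets a count and a proportion, both of which must be met before accrual stops: "if more than 2 patients are unable to receive all three infusions and more than 30% of the patients are unable". Neither condition names an arm, and both refer only to patients who are unable.

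The operating characteristics come next, for a wider event that takes in refusal. The chance of stopping is put at 4% for a failure rate of 8%. For the unacceptable rate the plan gives, from 1000 simulations, "a 82% chance of stopping early if 33% are unable or unwilling to receive all three infusions". Again no arm is named.

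The two safeguards that come next do name Arm B: an accrual hold if 3 of the first 10 patients cannot start Sipuleucel-T, and a toxicity review. The section then gives the purpose: "These rules are in place to limit patient exposure to arm B if it proves poorly tolerated or too toxic".

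The primary endpoint is worded in two ways. Sections 1.0 and 13.1 refer to patients able or willing to have all three infusions. The synopsis endpoint is the "percent of patients able to receive all three infusions of Sipuleucel-T following radiation therapy", with no mention of willingness. Both versions concern patients given radiation.

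**The concern.** The rule as written and the probabilities attached to it do not describe the same count. They differ in two respects.

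- **Which patients.** The trial randomises 50 patients 1:1. If the rule is run over everyone, Arm A patients who tolerate treatment well dilute the failures in Arm B.
- **Which failures.** If only inability is counted, refusals drop out, although 13.1 treats willingness as part of tolerability and 5.2.2 lists patient preference as a reason for leaving treatment.

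Section 7.2 makes the Protocol Management Team responsible for implementing stopping rules, and that team needs a rule it can count. Suppose 8 of 20 Arm B patients and 2 of 20 Arm A patients have failed. Arm B alone stands at 8/20 = 40% and accrual stops. Pooled, the figure is 10/40 = 25% and accrual continues. Among the Arm B safeguards, this is the only rule with stated probabilities.

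**Working it through.** **Inputs.** From 13.3: at least 3 failures and strictly more than 30%, checked at any time; failure rates of 8% (historical) and 33%; 25 patients per group. From the synopsis and 13.2: 50 patients, 1:1. The documents do not give the split of failures into unable and unwilling, or any Arm A failure rate other than the historical 8%.

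**Method.** Let q(n,k) be the probability that accrual is still open after n patients with k failures. Then

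q(n,k) = q(n−1,k)·(1−p) + q(n−1,k−1)·p,

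and any mass with k ≥ 3 and k > 0.30·n is moved to stopped. The stopping counts are 3 failures up to patient 9, 4 for patients 10–13, 5 for 14–16, 6 for 17–19, 7 for 20–23, and 8 at 24 and 25.

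**Step 1: reproduce the plan's figures.**

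| Patients, all at one failure rate | Stop at p = 0.08 | Stop at p = 0.33 |
|---|---|---|
| 25 | 3.6% | 82.4% |
| 50 | 3.6% | 89.9% |
| Stated | 4% | 82% |

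The row for 25 matches both figures. The 4% does not separate the two readings, because both give 3.6%. The 82% does. The Monte Carlo standard error for 1000 simulations is √(0.82 × 0.18/1000) = 0.0121, and (0.899 − 0.820)/0.0121 ≈ 6.5 standard errors. The simulation was evidently of 25 patients in one arm, with inability and refusal both counted.

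**Step 2: pool both arms, counting all failures.** With Arm A at 8% and Arm B at 33%, the average rate is (0.08 + 0.33)/2 = 20.5%, well under the 30% boundary.

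- Recursion with n = 50 and p = 0.205: 42.1%.
- Simulation, 25 per arm in random order, 100,000 runs: 42.0%.
- Strictly alternating arms: 37.5% (A first) or 43.7% (B first).
- Arm A assumed to fail at 5% or 15%, Arm B at 33%, 40,000 runs each: 34.5% or 58.2%.

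**Step 3: Arm B only, counting inability alone.** The share of failures due to inability is assumed, so this step is an illustration only.

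| Assumed share unable | Rate counted | Chance of stopping |
|---|---|---|
| 90% | 0.33 × 0.90 = 0.297 | 73% |
| 75% | 0.33 × 0.75 = 0.2475 | 56% |
| 50% | 0.33 × 0.50 = 0.165 | 24% |

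**Step 4: check the intended arm against the text.** Section 13.3 says the hold raises the chance of early stopping slightly, because three failures in ten reach 30% without exceeding it. If the hold is treated as a stop at 3 failures within the first 10 of 25 patients, the results move from 3.6% and 82.4% to 4.4% and 83.5%. That is a slight rise, as the section says.

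**The case against.** The strongest reply is that the section already settles both matters.

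On the arm, the remark about 3 of 10 sets Arm B patients directly against the 30% boundary, which makes sense only if the 30% is a share of Arm B. The purpose sentence names Arm B, and the primary endpoint concerns irradiated patients. On the event, the sentence giving the 4% and 82% follows the rule immediately and includes refusal. The hold rule uses the same shorthand: it speaks of patients unable to initiate, then compares them with a published rate for patients unwilling or unable to begin.

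Most of this stands. Arm B with all failures counted is the evident intent, so the 42% describes a literal application and not what the authors meant. What does not stand is the step from intent to rule. The operative sentence defines neither its numerator nor its denominator by arm, and its neighbours do name the arm. The synopsis also omits willingness, so the ambiguity about refusals is not confined to one sentence.

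A reader might infer that the 82% is a computational error. The documents do not support that, because it reproduces for the intended rule. A reader might also infer that Arm B has no other protection. It has the 3-of-10 hold, a toxicity review after 10 treated Arm B patients, and a review after any related grade 3 or higher toxicity on Arm B. The hold, however, concerns starting Sipuleucel-T and not completing three infusions, and no probabilities of its own are stated for it.

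**Conclusion.** The wording is defective and should be corrected; the simulation is sound. The 4% and 82% are right for 25 Arm B patients with inability and refusal both counted (exact 3.6% and 82.4%).

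Applied literally to all 50 patients, the rule would stop about 42% of the time when Arm B fails at 33%, roughly half the stated chance. That figure uses only the plan's own 8%, 33%, 25 per arm and 1:1 allocation, with patients in random order. The wider range of about 35% to 58% rests on assumed Arm A failure rates of 5% to 15%.

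The effect of leaving out refusals has a known direction but no known size. The 73%, 56% and 24% depend on assumed shares and should not be read as estimates for this trial.

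**What to change.** Reword the rule in 13.3 along these lines: *accrual will stop at any time if more than 2 Arm B patients, and more than 30% of Arm B patients, are unable or unwilling to receive all three infusions.* Keep the 4% and 82%, and label them as properties of this rule for 25 Arm B patients.

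The cost is one sentence and a label. No patients, visits, analyses or new simulations are needed. Whether patients replaced under section 6.0 count towards the rule is a separate question, on which this point does not depend.

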5.3 Subject Follow-Up

Following completion of therapy patients will be followed clinically and will undergo periodic laboratory and radiographic tests until week 60 or until disease progression requiring additional therapy (see Study calendar 10.0)

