9.1 Blood Collection

ALL SUBJECTS

100ml total whole blood (90mL collected in sodium heparin vacutainer tubes and 10mL collected in no-anticoagulant vacutaine tubes- from Becton Dickinson) collected at each time point specified in the study calendar (pre-study, and during weeks 4, 12, 24, 36, 48, and 60) will be sent to:

Send the sample(s) **priority overnight** via FedEx Next Day to:

Dendreon Corporation

Attention: Clinical Immunology

[name]

[contact]

ONLY SUBJECTS RECEIVING RADIATION AT CITY OF HOPE

10ml of the whole blood in the BD Vacutainer CPT tube (with Heparin) will collected at baseline (week 0) and at week 4 after radiation to be sent to the laboratory of [name] within 4 hours of collection to avoid degradation of the phosphomoieties (i.e., pSTAT3) assessed in this protocol. CPT tubes will be centrifuged at 1800g (approximately 2800 rpm on a Sorvall RT6000 centrifuge) for 20 min. at room temperature. After centrifugation, plasma in the CPT tubes will be gently pipetted against the gel plug to dislodge cells stuck to the top of the gel. The cell suspension will be transferred to a 50 mL conical polypropylene tube. cRPMI will be added to a total of 40 mL. A 10 mL aliquot of cell suspension for counting will be removed. The 50 mL tubes will then be centrifuged at 250g for seven minutes at room temperature. When centrifugation is complete, the supernatant will be aspirated. PMBCs will be either cryopreserved or used fresh.

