9.2.3 Humoral response assays

Antibody responses against PA2024 and PAP are determined by means of standard antibody ELISA (enzyme-linked immunosorbent assay). 96 well flat bottomed plates are coated with either PA2024, PAP or Tetanus (an assay control, and measure of immunocompetence) overnight, after which time plates are blocked with PBS/casein and then washed with PBST. Serially diluted serum is then added in duplicate to each set of plates and incubated at room temperature for 2 hours, after which time plates are washed with PBST and then incubated with a mixture of anti-IgM and anti-IgG (Jackson ImmunoResearch) for an hour. After this time plates are washed again with PBST and then incubated for an hour with horse radish phosphatase conjugated anti IgG+anti-IgM. Plates were further washed with PBST and O-phenylenediamine dihydrochloride substrate (Sigma) was then added for 15 minutes after which the developing reaction was stopped by the addition of $50 \mu\text{l}$ /well of 2N HCL (Sigma). Plates were read on a Synergy HT spectrophotometer (BioTEK) at 492 nm and the endpoint titer was determined as being the last dilution of serum that yielded an O.D. reading equivalent to assay background.

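### The only powered immune comparison cuts the PAP antibody titre at 400, names no time point and leaves the pre-study titre unused; a graded, baseline-adjusted analysis would be a cheap improvement

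*Combined protocol and SAP*

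**What the plan says.** Section 13.3 takes its control rate from the earlier phase III trial: "titers of antibodies against prostatic acid phosphatase exceeded 400 in 28.5% of the patients treated with Sipuleucel-T". On that basis "a Fisher's exact test with a 0.200 one-sided significance level will have 86% power" to separate a "non-radiation proportion, 0.285 and a radiation-treated group proportion of 0.570 when the sample size in each group is 25". It then considers a smaller effect, "if the true proportion about 400 is 28.5% in the control arm, and 48.5% in the radiation arm". For that effect it gives only the chance that the control arm looks better and the chance that the observed difference passes 8%, not the power of the test. The synopsis fixes the numbers: "Total Sample size is 50 randomized in a 1:1 fashion to Arm A and B".

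The data are richer than a yes/no result. Section 9.2.3 describes an ELISA on serially diluted serum in which "the endpoint titer was determined as being the last dilution of serum that yielded an O.D. reading equivalent to assay background". Section 9.1 has blood for all subjects "collected at each time point specified in the study calendar (pre-study, and during weeks 4, 12, 24, 36, 48, and 60"). Section 5.3 follows patients "until week 60 or until disease progression requiring additional therapy".

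Section 13.3 does not say at which week, or over which weeks, the titre must exceed 400. It describes no analysis of the titre as a graded quantity and no use of the pre-study value. It calls the between-arm analysis exploratory and restricts it to patients who start Sipuleucel-T.

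**The concern.** The trial's hypothesis (section 2.1) is that radiation enhances the immune response to Sipuleucel-T, and immune response is the first secondary objective. With 25 patients per arm, reducing a titre to above or below 400 can discard information that has already been collected. Fisher's test on counts this small also spends less than its nominal significance level.

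The missing time point is a separate gap. Week 12, any time after baseline and last available sample are all consistent with section 13.3, and the choice could be made after the data are seen. If any time is meant, the number of chances to exceed 400 depends on how long a patient stays in follow-up, and section 5.3 ties that to progression.

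At stake is how often this comparison would detect a true immune effect, and whether a graded analysis added later would count as planned or post hoc. The feasibility endpoint is not affected.

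**Working it through.** **Inputs from the documents.** Control proportion 0.285; radiation proportions 0.570 and 0.485; 25 per arm; Fisher's exact test, one-sided 0.20 (all section 13.3).

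**Inputs assumed.** The documents give no distribution or standard deviation of the titre and no correlation between pre-study and later titres. Everything about a graded test therefore rests on assumptions, varied below.

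**1. The plan's own figure.** Power is the sum, over all pairs (x, y) whose hypergeometric upper-tail p-value is at most 0.20, of Bin(x; 25, p1) × Bin(y; 25, p2).
- 0.285 vs 0.570: 86.0%. The stated 86% reproduces.
- 0.285 vs 0.485: 67.4%.
- 0.285 vs 0.285: 13.6%. This is the actual size, against a nominal 20%.

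The shortfall in size comes from discreteness. With 7 of 25 above the cut on Arm A, 10 of 25 on Arm B gives p = 0.276 and 11 gives p = 0.189, with nothing in between.

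**2. Graded test if radiation shifts the whole distribution.** Assume log titre is normal with equal SD. The shift that moves 28.5% above the cut to 48.5% is d = z(0.485) - z(0.285) = -0.038 + 0.568 = 0.530 SD. The noncentrality is 0.530 × sqrt(25/2) = 1.875 on 48 df.
- Unadjusted t-test at one-sided 0.20: 84.8%, a gain of 84.8 - 67.4, about 17 points.
- The same t-test run at Fisher's actual size of 13.6%: 77.8%. So about 10 points (77.8 - 67.4) come from cutting the titre and about 7 (84.8 - 77.8) from Fisher's unused significance level.
- Rank test by simulation, with titres piled up at an assay floor:

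| Share of control titres at floor | Power | Gain over Fisher |
|---|---|---|
| none | 82.9% | +15 |
| 31% | 82.5% | +15 |
| 50% | 80.8% | +13 |
| 62% | 79.3% | +12 |
| 69% | 77.3% | +10 |

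Under a whole-distribution shift the range is thus about 77 to 85%, a gain of roughly 10 to 17 points. At 28.5% vs 57% (d = 0.744) the t-test has 96.3% against 86.0%, about 10 points.

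**3. Graded test if radiation only raises the responder fraction.** By simulation at 28.5% vs 48.5%, one-sided 0.20:
- Non-responders at the floor, responders graded: rank test about 72%, t-test about 70%.
- Titres graded on both sides of the cut, only the fraction above it changing: rank test about 65%, t-test about 62 to 71% according to the spread assumed on each side.
- Two normal groups 3 SD apart: rank test about 63%, t-test about 64%.

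Over the shapes tried, power ran from about 61% to 72%. Against 67.4% that is -6 to +5 points.

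**4. Adding the pre-study titre.** With correlation rho, the effect becomes d / sqrt(1 - rho²) on 47 df. Under the shift model of step 2 at 48.5%:
- rho = 0.3: 86.8%, or 2 points above the unadjusted t-test.
- rho = 0.5: 90.6%, or 6 points.
- rho = 0.7: 96.2%, or 11 points.

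None of the 10 to 17 points in step 2 comes from the baseline; these are additional. The values of rho are illustrative.

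**The case against.** The best defence is that the comparison does not carry the trial. The primary objective is feasibility, section 13.3 labels the between-arm analysis exploratory and meant to motivate later studies, and nothing in it forbids a graded analysis. A cut that matches a published reference is a legitimate responder definition, and the 86% is right. All of this stands. It lowers the weight of the point but does not remove the benefit of specifying an analysis of data already in hand.

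The second defence is that the gain is conditional. Section 2.1 reports PAP antibodies in 28.5% of Sipuleucel-T patients and 1.4% on placebo, which fits responders and non-responders as well as it fits a shift. This also stands, and step 3 shows that the gain can then vanish or turn slightly negative. The low placebo rate further suggests that pre-study titres may cluster near the floor and predict later ones only weakly.

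Third, the time point might be inferred: section 2.1 counts PA2024 titres above 400 at any time after baseline, and the PAP result follows in the same paragraph. But the phrase is attached to PA2024, and section 13.3 does not repeat it.

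A reader might also infer that an any-time count over unequal follow-up would seriously inflate the false-positive rate. The documents do not support a figure. They give no between-arm difference in the number of samples and no dependence between samples from one patient. The week-4 sample also falls on Day 22, the day of the first infusion in the study schema, so it cannot be treated like later ones.

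**Conclusion.** The point holds as a missed efficiency and an unstated time point, not as an error in the power statement. Fisher's test has 67% power at the plan's second scenario and an actual size of 13.6%. A graded test would gain roughly 10 to 17 points there if radiation moves the whole log-titre distribution, and about nothing (-6 to +5) if it only enlarges the responder fraction. The documents do not say which is likelier.

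It is tempting to conclude that the cut and the unused baseline together cost a fixed 17 points. That is not supported: 17 is the upper end, it compares Fisher with an unadjusted t-test under assumed normality, about 7 of those points are Fisher's discreteness, and none come from the baseline. Baseline adjustment may add more, by an amount that depends on an unknown correlation. This is a cheap improvement.

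**What to change.** In section 13.3, prespecify a between-arm comparison of PAP titre at week 12, the first scheduled immune sample after all three infusions. Analyse log titre by ANCOVA with arm and pre-study log titre, or use a baseline-stratified rank test if many values sit at the lowest dilution. State in advance what triggers the switch.

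Keep Fisher's test on titre above 400, at a stated time point, as the responder analysis. Note that a week-12 proportion may not match the 28.5% reference if that reference was counted at any time after baseline.

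The cost is SAP wording and minor programming; no added patients, visits or samples. Two conventions are needed: one for titres below the lowest dilution, and one for missing week-12 samples, including those of patients who leave follow-up early. The power gain should not be promised, since it depends on how radiation acts on the titre.
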